#### 4. STUDY DESIGN

# 4.1. General Description

This is a Phase 1, open-label, dose-escalation, 2-part study in adult patients with advanced malignancies known to overexpress the WT1 protein. The study will primarily evaluate DLT and define the MTD of WT2725 Dosing Emulsion during the DLT Evaluation Period, which extends from the day of the first dose of study drug to just prior to the fifth dose (Days 1 - 29). In addition, antitumor activity and biomarkers indicative of immune response will be evaluated from the first dose until discontinuation of the patient from the study. An end of study assessment will take place within 28 days after the last dose of study drug and prior to the start of alternate antineoplastic therapy.

The initial patients in each dose escalation cohort will be enrolled at least one week apart to evaluate initial safety from the first 2 patients, then a "rolling-six" design will be employed that allows accrual of 2 to 6 patients concurrently in each dose escalation cohort.

In Part 1 of the study, the 0.3 mg cohort will be conducted first. After safety and tolerability have been established for the first cohort, enrollment of subsequent patients will be conducted sequentially in subsequent cohorts and continue until the MTD or all planned cohorts are attained. Enrollment of each cohort may include patients with any of the eligible tumor types (see below). Enrollment of the highest tolerable dose cohort (MTD or highest planned cohort) will continue until there are at least 6 patients total in the study with each tumor type that are evaluable for DLT, biomarkers, and response. This dose is considered the recommended phase 2 dose (RP2D). Enrollment of up to 3 RP2D cohorts of 10 patients each of a specific tumor type may take place at this dose in order to further characterize the safety and efficacy of WT2725 Dosing Emulsion at this

dose in these subsets of patients. Additional dose escalation cohorts after the initial expansion cohorts may be enrolled if a MTD has not been determined and significant signs of toxicity have not been observed in the expansion cohorts.

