In Part 2 of the study, the 18.0 mg cohort will be conducted first. After safety and tolerability have been established for the 18.0 mg cohort, enrollment of subsequent patients will be conducted sequentially in the 27.0 mg cohort. Approximately 10 patients at each dose level (18.0 and 27.0 mg) with at least 4 patients with each malignancy type (glioblastoma and acute myeloid leukemia [AML]) will be enrolled at each of these dose levels. If the MTD is reached in Part 2 before the total of 20 patients are enrolled, remaining patients will be enrolled at the prior dose level. In the event that a dose level is excluded from further study due to dose limiting toxicity all patients may continue the study at the most recently completed dose without DLT, eg, if the 27.0 mg dose is excluded due to DLT all patients may continue at 18.0 mg.

Patients who have completed the consolidation phase of their assigned cohort and have not experienced a DLT,  $\geq$  Grade 2 study drug-related injection-site reaction, or required a dose reduction may have their dose escalated to that of the highest cohort for which safety and tolerability have been established. The expected time to enroll each dose escalation cohort (2 - 6 patients) is between 6 and 12 weeks.

Each part of the study will include 3 treatment phases based on intended timing of study drug dosing as indicated below (see Figures 1 and 2):

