Again, in subsequent dose escalation cohorts in Part 1, if 3 patients in a dose cohort complete the DLT Evaluation Period and there are no DLTs identified, then the dose level is increased, otherwise enrollment of additional patients (up to 3 more) may be permitted in the same cohort. If one of 3 patients in a dose escalation cohort experiences a DLT then up to a total of 6 patients are enrolled in the same dose cohort and dose escalation may only proceed if no additional patients experience DLT. Patients not evaluable for DLT assessment may be replaced.

In Part 2 of the study, the 18.0 mg cohort will be conducted first. If 3 patients in the dose cohort complete the DLT Evaluation Period and there are no DLTs identified, then the 27 mg dose cohort may begin, otherwise enrollment of additional patients (up to 3 more) may be permitted in the same cohort. If one of 3 patients in a dose escalation cohort experiences a DLT then up to a total of 6 patients are enrolled in the same dose cohort and dose escalation may only proceed if no additional patients experience DLT. After safety and tolerability have been established for the 18.0 mg cohort, enrollment of subsequent patients will be conducted sequentially in the 27.0 mg cohort. If additional patients are ready to enroll in the study prior to completion of the DLT Evaluation Period for the 27.0 mg dose cohort, up to a total of 10 patients may be enrolled at the 18.0 mg dose level. Approximately 10 subjects at each dose level (18.0 and 27.0 mg) with at least 4 patients with each malignancy type (glioblastoma and AML) will be enrolled. If the MTD is reached in Part 2 before the total of 20 patients are enrolled, remaining patients will be enrolled at the prior dose level. Patients not evaluable for DLT assessment may be replaced.

If at any time during dose escalation 2 or more patients experience DLT within a dose cohort that suggests that the MTD has been exceeded; no additional patients will be enrolled into that dose cohort and dose escalation will end. The MTD will be the dose level below that which resulted in 2 or more patients experiencing a DLT. If the suspected MTD is based on a cohort in which fewer than 6 patients were enrolled then additional patients will be enrolled and treated at that dose level until there is a total of 6 patients evaluable for DLT within that dose escalation cohort.

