# 8. STATISTICAL ANALYSIS

In this section and all after, when tables are presented by posttreatment visits, the last visit will be the visit at the end of study. When applicable, visits after the start of the maintenance phase and unscheduled visits will be included in a summary of maximum and minimum values observed for each patient's posttreatment visits, i.e., the minimum and maximum values are based on all the post treatment visits.

In general descriptive statistics for continuous variables will be summarized by the mean, standard deviation, 25th percentile, median (50th percentile), 75th percentile, minimum and maximum values. When continuous variables are displayed for less than 3 patients, only the number of observations will be presented. Categorical variables will be summarized using counts and percentages.

All raw data will be presented to the original number of decimal places. The means and medians will be presented to 1 more decimal place than the raw data. The standard deviations will be presented to 2 more decimal places than the raw data.

Baseline will generally be defined as data obtained as the last non-missing value prior to the first dose of study drug, i.e., including the pre-dose assessment on Day 1, assessments during screening and other assessments prior to the first dose of study drug.

AE tables and laboratory tables will be presented by visits and by tumor group. Tumor groups are defined as groups of overall, solid tumor, and AML patients.

Unless otherwise stated, summaries will be produced by dose cohort, which is defined as the intended and starting dose to which the patient was enrolled.

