#### 8.6.3.1. CTL Evaluation

A patient is considered a CTL responder if s/he has:

• Two or more post-baseline visits (no need to be consecutive) with >=2-fold increase from baseline, if the baseline is not 0,

Or

 Only one post-baseline visit with >=2-fold increase from baseline when the total number of post-baseline visits is <=4, if the baseline value is not 0,

 Or

• At least one post-baseline value > 0, if a patient has baseline of 0

A table will present the number and percentage of patients for their CTL response. Additionally, geometric mean, geometric SD, the mean, standard error (se), SD, median, 25 and 75 percentile of baseline assessments and the corresponding same descriptive statistics for both mean of post-baseline assessments for each patient and maximum of post-baseline assessments for each patient will be presented by dose cohort and overall, where geometric mean is

$$\mu_{\mathbf{g}} = \sqrt[n]{A_1 A_2 \cdots A_n}.$$

and geometric SD is

$$\sigma_g = \exp \sqrt{rac{\sum_{i=1}^n (\ln rac{A_i}{\mu_g})^2}{n}}.$$

The Wilcoxon singed-rank test will be performed to see the difference between the baseline assessments and the mean of post-baseline assessments for each cohort and overall as well as the difference between the baseline assessments and the maximum of post-baseline assessments for each cohort and overall. Bar plot of mean and SE of baseline and mean of post-baseline assessments will be presented as well as baseline vs. maximum of post-baseline assessments stratified by both dose cohorts and cancer types. Similar bar plots are generated for the median and quartiles.

The percent change from baseline will be presented over time graphically. A by-patient listing will be provided.

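### The geometric SD for CTL divides by n, which understates log-scale spread by 18.4% in a cohort of 3 and 5.1% in a cohort of 10; the effect is minor and confined to a descriptive row

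*SAP*

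**What the plan says.** SAP 8.6.3.1 plans a descriptive table for CTL containing "geometric mean, geometric SD, the mean, standard error (se), SD, median, 25 and 75 percentile of baseline assessments". The same set is given for each patient's mean post-baseline value, and the "maximum of post-baseline assessments for each patient will be presented by dose cohort and overall". Two formulas follow. The geometric mean is the n-th root of the product of the n values. The geometric SD is the exponential of the square root of the sum of squared ln(A_i / geometric mean), divided by n. The text does not comment on the divisor.

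Three other places fix the sample sizes at which this will be printed:

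- SAP 4.1 describes a rolling-six design that "allows accrual of 2 to 6 patients concurrently in each dose escalation cohort".
- SAP 4.1.1, for the later Part 1 cohorts: "if 3 patients in a dose cohort complete the DLT Evaluation Period and there are no DLTs identified, then the dose level is increased". A cohort can therefore close at 3. Part 2 plans about 10 per dose level.
- SAP 8: "When continuous variables are displayed for less than 3 patients, only the number of observations will be presented". The smallest cohort for which a geometric SD is shown is therefore 3.

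The CTL responder rule in 8.6.3.1 includes the case "At least one post-baseline value > 0, if a patient has baseline of 0", so the plan expects some CTL values of exactly zero.

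**The concern.** The deviations are taken around a geometric mean computed from the same patients, so they carry n-1 degrees of freedom. Dividing by n gives the population form, which is too small on average when the values are a sample. The shortfall depends only on n and is largest where n is smallest. Since the statistic is printed side by side for dose cohorts of 3 to about 10 patients, or more at 9.0 mg if the expansion cohorts fill, part of any visible difference in spread between columns would come from cohort size and not from the dose. What is at stake is how one descriptive row is read.

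**Working it through.** The documents give no geometric SD value, so there is no stated figure to reproduce. The check is of the formula.

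**Inputs.** Divisor n (SAP 8.6.3.1). Smallest displayed n = 3 (SAP 8). Escalation cohorts of up to 6 (SAP 4.1). About 10 per dose level in Part 2 (SAP 4.1). Up to 3 expansion cohorts of 10 at the recommended dose (SAP 4.1), which is 3 × 10 = 30 if all are filled.

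**Step 1: exact ratio.** With S the sum of squared log deviations, the SAP's log-scale SD is sqrt(S/n) and the sample SD is sqrt(S/(n-1)). Their ratio is sqrt((n-1)/n), whatever the data.

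| n | sqrt((n-1)/n) | Understatement, log scale |
|---|---|---|
| 3 | 0.8165 | 18.4% |
| 4 | 0.8660 | 13.4% |
| 5 | 0.8944 | 10.6% |
| 6 | 0.9129 | 8.7% |
| 10 | 0.9487 | 5.1% |
| 30 | 0.9832 | 1.7% |

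**Step 2: the printed scale.** The printed value equals the n-1 value raised to the power sqrt((n-1)/n). The documents give no CTL spread, so the starting values are assumptions chosen to show a range.

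| Geometric SD with n-1 (assumed) | Printed at n=3 | n=6 | n=10 |
|---|---|---|---|
| 1.5 | 1.39 | 1.45 | 1.47 |
| 2.0 | 1.76 | 1.88 | 1.93 |
| 3.0 | 2.45 | 2.73 | 2.84 |
| 5.0 | 3.72 | 4.35 | 4.60 |

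At n=3 the printed figure is lower by 7%, 12%, 18% and 26% respectively.

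**Step 3: how much of the size effect n-1 removes.** Assume log-normal CTL values with equal true spread in every cohort. The expected sample SD of the logs, as a fraction of the truth, is c4 = sqrt(2/(n-1)) × Γ(n/2) / Γ((n-1)/2). With divisor n this is multiplied by the Step 1 ratio.

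| n | Divisor n | Divisor n-1 |
|---|---|---|
| 3 | 0.724 | 0.886 |
| 6 | 0.869 | 0.952 |
| 10 | 0.923 | 0.973 |

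The gap between cohorts of 3 and 10 is 0.923 - 0.724 = 0.199 with n, and 0.973 - 0.886 = 0.087 with n-1. The change removes more than half of the gap, not all of it.

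Simulation under the same assumption (200,000 runs):

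| Comparison | Cohort of 3 has the smallest spread, divisor n | Divisor n-1 | Neutral |
|---|---|---|---|
| 3 against 10 | 69% | 59% | 50% |
| 3 against 6 | 64% | 57% | 50% |
| 3, 6 and 10 | 55% | 47% | 33% |

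**Step 4: zeros.** If one value in a row is 0, the product is 0 and so is the geometric mean. The log ratios are then undefined for that patient and infinite for the others, so no geometric SD exists with n or n-1. In the baseline row this happens as soon as one patient has a baseline of 0. In the post-baseline rows it happens when all of a patient's post-baseline values are 0. SAP 8.6.2.3 gives a substitution rule for undetectable WT1 RT-PCR results; 8.6.3.1 gives none for CTL.

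**The case against.** Divisor n is a written-out definition of a descriptive statistic, reproducible and exactly convertible by any reader. It is understated only if read as an estimate of population spread. That is fair, and it is why this is not a calculation error with consequences downstream. But the SAP does not label the figure as a population form, and a reader of a cohort summary will normally take an SD as an estimate.

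Nothing else in the plan uses the figure. The responder rule works on fold-change from baseline. The Wilcoxon signed-rank test "will be performed to see the difference between the baseline assessments and the mean of post-baseline assessments for each cohort and overall", and likewise for the maximum. The bar plots show mean and SE, or median and quartiles. The MTD rests on DLT incidence and the overall safety profile (SAP 6.2). The arithmetic SD, quartiles and a by-patient listing are also provided, and with 3 patients the listing shows every value. All of this stands.

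Three stronger readings are tempting and are not supported:

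- A reader might infer that the smallest cohorts will look the most uniform. Step 3 shows only a tendency, part of which is ordinary small-sample behaviour that remains with n-1.
- A reader might infer that the arithmetic and geometric SDs use different divisors in one table. The SAP gives no divisor for the arithmetic SD, so this rests on assumed software defaults. The two are also on different scales, one in assay units and one a ratio.
- A reader might infer that the main immune endpoint is affected. SAP 6.3 lists CTL as one of four immune measures without ranking them, and its evaluation sits under exploratory analyses in 8.6.3.

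**Conclusion.** The point holds as a minor correction. As an estimate of spread, the geometric SD in SAP 8.6.3.1 is too small on the log scale by a known factor, at worst 18.4% (n=3, the smallest cohort displayed), 8.7% at n=6 and 5.1% at n=10. These percentages are exact and need no distributional assumption. The statement that smaller cohorts tend to look more uniform assumes log-normal values with equal true spread. The plan contains no comparison of spread between doses, so a reader who infers that a dose conclusion is at risk goes beyond the documents. The missing rule for zeros is the more practical gap in the same formula, because it can leave the row with no value at all.

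**What to change.** In SAP 8.6.3.1, replace n with n-1 in the geometric SD, that is, define it as exp of the sample SD of the log values, and apply this to the baseline, mean post-baseline and maximum post-baseline rows. Log-scale values then rise by sqrt(n/(n-1)): 1.225 at n=3, 1.095 at n=6 and 1.054 at n=10. A footnote naming the divisor would be a lesser remedy: it makes the figure interpretable but leaves the dependence on cohort size unchanged.

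In the same edit, state how CTL values of 0 enter the geometric mean and geometric SD, either by a stated substitution or by restricting these two statistics to non-zero values, and print the number of zeros in each row. The documents give no CTL detection limit, so the sponsor would have to supply the value for any substitution.

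The cost is one symbol in the formula, one sentence on zeros and the matching program change. No new data are needed and no other analysis changes.

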5. AMENDMENT NO. 3, PROTOCOL VERSION 4.0 (27 MAR 2013)

The following changes were made to the protocol:

- In order to more completely assess disease progression and patient survival, these parameters will continue to be assessed every 3 months following the end of study visit.
- As patients with Grade 2 hematology values may be enrolled in the study and hematologic toxicity has not been observed with WT2725 during this study, the dose-limiting toxicity definition related to hematology parameters has been revised to include at least a 2 grade shift.
- It is not currently known whether administering and evaluating a DTH skin test immediately associated with vaccination or remote from vaccination correlates best with other outcomes. In order to assess and compare both methods, additional DTH skin tests were added at Days 1, 29, and 85, which resulted in adding visits at Days 31 and 87 to evaluate the DTH skin tests. In order to limit the visit schedule burden on patients, Day 2 assessments were moved to Day 3 to coincide with DTH skin test evaluation from Day 1.
- In order to increase the precision of the baseline CTL value upon which changes at subsequent time points are determined, an additional baseline CTL blood sample was included during screening.
- Results of an additional historical tumor assessment prior to baseline, if available, are requested in order to provide more information on tumor progression rate.

- In order to limit testing to patients with a reasonable possibility of a positive result, clarification was provided regarding when hepatitis B and C, human immunodeficiency virus (HIV) 1, and HIV 2 testing are required at screening.
- In order to be consistent with tumor marker response criteria, the window for collection of tumor markers during screening was shortened to 14 days prior to first dose.
- As hematologic toxicity with WT2725 has not been demonstrated in this study, the inclusion criteria for bone marrow and immune reserve was revised by lowering required absolute neutrophil count from $\geq 1500/\mu\text{l}$ to $\geq 1000/\mu\text{l}$, platelets from $\geq 10.0 \times 10^4/\mu\text{l}$ to $\geq 5.0 \times 10^4/\mu\text{l}$ after stem cell transplant, and absolute lymphocyte count (ALC) from $\geq 1000/\mu\text{l}$ to $\geq 500/\mu\text{l}$ after stem cell transplant in order to allow enrollment of a greater and more relevant patient population.

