Hematology/ serum chemistry f	X c	X c	X c		X c		X c		X	
Urinalysis	X c	X c	X c		X c		X c		X	
12-lead ECG		X c			X c		X c		X	
DTH skin test injection				$X^g$	$X^{g,h}$			X g		
DTH skin test evaluation					X i	X j			X j	
Blood sample for CTL	X c	X c	X c		X c		X c		X	

<sup>s Tumor markers drawn from peripheral blood samples should be assessed at least every 4 weeks after the 1st dose but may be performed more frequently (For other tumor assessments, perform every 8 weeks after 1st dose or more frequently as clinically indicated).

Table 2: Schedule of Assessments for Consolidation Phase, Maintenance Phase, and End of Study – Part 1 (Continued)

	Consolidati	ion Phase a,b					Maintenanc e Phase a,b	End of Study	y b	Follow-up
	6 th dose	7 th dose	8 th dose		9 th dose					
	Day 43 (±2)	Day 57 (±2)	Day 71 (±2)	Day 83	Day 85 (±2)	Day 87	every 28 (+7) days	48 hours before End of Study Visit	within 28 days after last dose	every 3 months
Blood sample for Anti- WT1 antibody		X c			X c		X c,k		X	
Blood sample for retrospective biomarker analyses		X c			X c		X c,k		X	
Blood sample for PBMC isolation									X	
IHC tumor samples									X¹	
Tumor assessment		X c,m			X c,n		X c,m		X m	
Adverse events							•	•	•	
Concomitant medications										
Disease Progression/ Survival				107.000					Xº	Xº

Abbreviations: AML = acute myeloid leukemia, CA-125 = cancer antigen 125, CTL = cytotoxic T lymphocyte induction activity, DTH = delayed-type hypersensitivity reactivity, ECG = electrocardiogram, ECOG = Eastern Cooperative Oncology Group, FSH = follicle-stimulating hormone, HLA = human leukocyte antigen, IHC = immunohistochemistry, irRC = immune-related response criteria, IWG = International Working Group response criteria in acute myeloid leukemia, MRI = magnetic resonance imaging, PBMC = peripheral blood mononuclear cell, PET = positron-emission tomography, RT-PCR = reverse transcriptase-polymerase chain reaction, SPECT = single-photon emission computed tomography, WT1 = Wilms' tumor gene product 1

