## 8.3. Analysis Populations

There are 3 planned analysis populations.

- Safety population: includes all enrolled patients who receive at least 1 dose of study drug and will be used for the analysis of all safety and efficacy data except as noted below
- DLT population: includes all patients in the Safety population who experience a DLT within the DLT evaluation period or completed the DLT evaluation without experiencing a DLT and will be used for analysis of DLT.
- Efficacy population: include all patients in the Safety population who are evaluable for response (for each irRC, IWG, CA-125 and WT1 by RT-PCR)
  - o Population for irRC response: including all the patients in the Safety population who are not AML patients and whose lesions are measureable and have at least one posttreatment assessment. (Note that any posttreatment irRC assessment is based on the baseline assessment)
  - O Population for modified IWG response: includes all the AML patients in the Safety population who have >5% marrow blasts or >50 copy/μ g RNA of quantitative RT-PCR for WT1 transcript before the first date/time of study drug and who have at least one posttreatment assessment.
  - o Population for CA-125 tumor marker: including all ovarian cancer patients in the Safety population who have a baseline CA-125 assessment and at least one assessment posttreatment.
  - Population for WT1 by RT-PCR tumor marker: includes AML patients in the Safety population who have a baseline assessment and at least one assessment posttreatment.
- Population for CTL: including all patients in the Safety population who has a baseline assessment of percentages of WT1-positive cells among CD8-positive cells and at least one post-baseline assessment

Additional populations for analyses of other tumor markers identified may be defined in a similar manner.

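### The signed-rank test of one baseline CTL value against a raw mean of many later values tilts toward a rise if CTL is right-skewed within patients across visits

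*SAP*

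**What the plan says.** SAP 8.6.3.1 states that "The Wilcoxon singed-rank test will be performed" on "the difference between the baseline assessments and the mean of post-baseline assessments for each cohort and overall". The same sentence plans a second comparison, with the post-baseline maximum, which is not the subject here. No transformation, significance level or sidedness is given for the test. The geometric mean and geometric SD appear there only as descriptive statistics, next to the arithmetic mean, SD, standard error, median and quartiles.

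On baseline, SAP section 8 says: "Baseline will generally be defined as data obtained as the last non-missing value prior to the first dose of study drug". By default that is one value per patient. Two pre-dose CTL samples are nevertheless collected. Protocol Amendment No. 3 added a screening sample "In order to increase the precision of the baseline CTL value upon which changes at subsequent time points are determined", and SAP Tables 1 and 3 show both the screening and the Day 1 sample. Nothing in the SAP says the two are averaged.

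On the post-baseline side, SAP 8.3 requires a "baseline assessment of percentages of WT1-positive cells among CD8-positive cells and at least one post-baseline assessment", so a patient may contribute as few as one later value. Most patients who stay on treatment contribute far more.

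**The concern.** The signed-rank test is often read as a test of no change. Its null is narrower: each patient's difference must be symmetric about 0. Here the difference sets one draw against an average of many. A single draw from a right-skewed distribution usually lies below the mean of several draws from that distribution. Most differences are then positive although nothing has changed.

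CTL induction is a secondary endpoint variable (SAP 6.3), and the study has no control arm (SAP 4.2). The before-and-after test therefore carries most of the inferential weight for a claim that vaccination raises CTL. A reader who rightly discounts the comparison with the maximum would take the comparison with the mean as the fair one. The tilt also costs power to detect a true fall.

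**Working it through.** **Inputs from the documents**
- Baseline values per patient: 1 (SAP section 8, default rule).
- Post-baseline draws, from the "Blood sample for CTL" row of SAP Tables 1 to 4. Part 1: Days 8, 15, 22, 29, 43, 57, 71 and 85, so K = 8, plus maintenance and end of study. Part 2: 8 by Day 57 and about 14 by Day 141 (that table row is broken in the text).
- Patients: 60 to 80 dosed overall and about 10 per Part 2 dose level. The escalation design "allows accrual of 2 to 6 patients concurrently in each dose escalation cohort".

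**Inputs assumed**
- Two-sided 5% level.
- Log-normal CTL with between-patient log SD 1.0.
- Within-patient log SD s from 0.3 to 1.0. The corresponding CV is √(exp(s²) − 1).

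The plan states no error rate or power for this test, so there is no figure to reproduce.

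**Step 1: why symmetry fails.** Let D = mean(X₁…X_K) − X₀, with no vaccine effect and independent draws around the patient's own level. Let κ be the within-patient third central moment.
- The mean of D is 0.
- The third central moment of D is κ/K² − κ = κ(1/K² − 1).
- With K = 8 this is κ(1/64 − 1) = −(63/64)κ. Right skew (κ > 0) makes D left-skewed with mean 0, so for log-normal values its median lies above 0.
- With K = 1 it is 0. Simulation agrees: the test is then valid (4.7% to 5.2%).
- With two baseline samples averaged it is κ(1/64 − 1/4) = −(15/64)κ, which is smaller but not zero.
- If values are symmetric within patients, κ = 0 however skewed the patients are against each other. Simulation again agrees (4.5% to 5.2%).

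**Step 2: size in the overall test.** Simulated rejection under no effect, n = 60 and K = 8. Ranges cover separate simulation runs.

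| s | CV | Independent draws | Serial correlation 0.8 |
|---|---|---|---|
| 0.3 | 0.31 | 7–9% | about 6% |
| 0.5 | 0.53 | 14–15% | about 7% |
| 0.7 | 0.80 | 24–27% | 8–10% |
| 1.0 | 1.31 | 41–43% | 13–15% |

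With independent draws nearly all rejections point to a rise. At CV 0.5, for example, the total of 13.8% splits into 13.6% false rises and 0.2% false falls. The chance that a patient's difference is positive is 0.55, 0.58 and 0.63 at CV 0.3, 0.5 and 1.0, instead of 0.50.

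**Step 3: other settings (no effect)**
- n = 10, K = 8: about 5–11%.
- n = 80, K = 8: 17.0% at CV 0.5 and 42.5% at CV 1.0.
- Mixed 2 to 10 draws per patient, n = 60: 9%, 13%, 18% and 31% at s = 0.3, 0.5, 0.7 and 1.0.
- Both baseline samples averaged, n = 70, K = 8: 9.3% at CV 0.5 and 17.7% at CV 1.0.
- Low Poisson counts with zeros, n = 60, K = 8: from 15% (mean 0.3) to 8% (mean 1).

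**Step 4: replacements under the same null**
- Signed-rank on mean(log post-baseline) − log(baseline): about 4–6% at serial correlation 0 to 0.8. It fails when zeros dominate. For Poisson counts with mean 0.3 (at least exp(−0.3) = 74% zeros), adding an offset of 0.1 before taking logs gives about 13%.
- Patient-stratified rank test (van Elteren): about 5% with independent draws, including data with zeros, but about 6.5–8% at serial correlation 0.8.
- Log of the arithmetic mean is not a remedy. At n = 70 it rejects in 33% (CV 0.5) and 74% (CV 1.0) of null trials.

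**The case against.** A reader might infer that the SAP itself treats CTL as right-skewed. It does not say so. Its geometric summaries are taken across patients and stand beside arithmetic ones, and skew across patients causes no bias. The 2-fold responder rule and the floor at zero suggest multiplicative variation within a patient, but they are hints, and no within-patient CV appears anywhere. This objection stands, and the conclusion must remain conditional.

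A reader might also take the independent-draw figures as the expected error rate. Samples 7 to 28 days apart may well be correlated, and baseline always comes first. At serial correlation 0.8 the excess is small up to s = 0.5. This stands too, so both columns of the table are needed.

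The baseline rule says only that it applies generally, and the second pre-dose sample was added for precision, so averaging may be intended. That would reduce the bias without removing it.

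The replacements have limits of their own. Under strong serial correlation the stratified rank test is no better than the planned test at s of 0.3 to 0.5.

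Finally, the test sits under exploratory analyses with no significance level or decision rule, and CTL is also reported by responder status, plots and listings. That limits the importance of the point but does not make the comparison fair.

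The smallest possible two-sided p-value is 2/2ⁿ, or 0.0625 at n = 5. A reader might call the small-cohort tests an error on that account. In a plan without a stated level this is a reporting note.

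**Conclusion.** The point holds conditionally. The planned test does not isolate a change in CTL: with right-skewed or multiplicative variation within patients it favours a rise when nothing has happened. In the overall test of 60 to 80 patients the excess ranges from negligible to severe, depending on within-patient variability and serial correlation, neither of which the documents give. At n = 60 the span is about 6% to 43% against a nominal 5%. In cohorts of about 10 it is modest.

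The documents do not support saying that a false CTL rise is expected, or that the study's main conclusions are at risk. The analysis serves a secondary immune-response endpoint and does not enter the DLT or MTD decisions. The change is still worth making: the planned test is never materially better at holding its level than a suitably chosen replacement, and it can be far worse.

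**What to change.** In SAP 8.6.3.1, replace the raw comparison of baseline with the post-baseline mean as follows.
- **Zeros rare:** signed-rank test on each patient's mean of log post-baseline values minus log baseline, with a stated way of handling the few zeros.
- **Zeros common:** rank test of baseline against post-baseline draws stratified by patient (van Elteren; Cochran-Mantel-Haenszel with modified ridit scores, patient as stratum). State that it is mildly liberal, at about 6.5–8%, under strong serial correlation.
- Define rare and common, and fix the rule for choosing between the tests before post-baseline data are reviewed.
- Say whether baseline is the last pre-dose value or uses both collected samples.

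The cost is SAP wording and a few lines of code, with no new data. The downside is fewer nominally significant rises. With n = 60, s = 0.7, independent draws and 2 to 10 draws per patient, a true 1.3-fold rise is declared in about 66% of trials by the stratified rank test, against 90% by the planned test, whose rate is inflated by the tilt. In the other direction, power for a true 20% fall goes from 14% to 52%.
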